6.7 BIOMARKER ANALYSES

Exploratory biomarker analyses may be performed in an effort to understand the association of these markers with study treatment response. The biomarker analysis will be descriptive in nature includes modulation of ER-target genes as well as ER and PR protein levels.

Although no formal statistical analysis of exploratory biomarkers will be performed, data may be analyzed in the context of this study and in aggregate with data from other studies.

7. DATA COLLECTION AND MANAGEMENT

7.1 DATA QUALITY ASSURANCE

The Sponsor will be responsible for data management of this study, including quality checking of the data. Data entered manually will be collected via EDC through use of eCRFs. Sites will be responsible for data entry into the EDC system. In the event of discrepant data, the Sponsor will request data clarification from the sites, which the sites will resolve electronically in the EDC system.

The Sponsor will produce an EDC Study Specification document that describes the quality checking to be performed on the data. Central laboratory data and IxRS will be sent directly to the Sponsor, using the Sponsor's standard procedures to handle and process the electronic transfer of these data.

eCRFs and correction documentation will be maintained in the EDC system's audit trail. System backups for data stored by the Sponsor and records retention for the study data will be consistent with the Sponsor's standard procedures.

7.2 ELECTRONIC CASE REPORT FORMS

eCRFs are to be completed through use of a Sponsor-designated EDC system. Sites will receive training and have access to a manual for appropriate eCRF completion. eCRFs will be submitted electronically to the Sponsor and should be handled in accordance with instructions from the Sponsor.

All eCRFs should be completed by designated, trained site staff. eCRFs should be reviewed and electronically signed and dated by the investigator or a designee.

At the end of the study, the investigator will receive patient data for his or her site in a readable format that must be kept with the study records. Acknowledgement of receipt of the data is required.

7.3 SOURCE DATA DOCUMENTATION

Study monitors will perform ongoing source data verification and review to confirm that critical protocol data (i.e., source data) entered into the eCRFs by authorized site personnel are accurate, complete, and verifiable from source documents.

Source documents (paper or electronic) are those in which patient data are recorded and documented for the first time. They include, but are not limited to, hospital records, clinical and office charts, laboratory notes, memoranda, patient-reported outcomes, evaluation checklists, pharmacy dispensing records, recorded data from automated instruments, copies of transcriptions that are certified after verification as being accurate and complete, microfiche, photographic negatives, microfilm or magnetic media, X-rays, patient files, and records kept at pharmacies, laboratories, and medico-technical departments involved in a clinical trial.

Before study initiation, the types of source documents that are to be generated will be clearly defined in the Trial Monitoring Plan. This includes any protocol data to be entered directly into the eCRFs (i.e., no prior written or electronic record of the data) and considered source data.

Source documents that are required to verify the validity and completeness of data entered into the eCRFs must not be obliterated or destroyed and must be retained per the policy for retention of records described in Section 7.5.

To facilitate source data verification and review, the investigators and institutions must provide the Sponsor direct access to applicable source documents and reports for trial-related monitoring, Sponsor audits, and IRB/EC review. The study site must also allow inspection by applicable health authorities.

7.4 USE OF COMPUTERIZED SYSTEMS

When clinical observations are entered directly into a study site's computerized medical record system (i.e., in lieu of original hardcopy records), the electronic record can serve as the source document if the system has been validated in accordance with health authority requirements pertaining to computerized systems used in clinical research. An acceptable computerized data collection system allows preservation of the original entry of data. If original data are modified, the system should maintain a viewable audit trail that shows the original data as well as the reason for the change, name of the person making the change, and date of the change.

7.5 RETENTION OF RECORDS

Records and documents pertaining to the conduct of this study and the distribution of IMP, including eCRFs, electronic or paper patient-reported outcome data (if applicable), Informed Consent Forms, laboratory test results, and medication inventory records, must be retained by the Principal Investigator for at least 15 years after completion or discontinuation of the study or for the length of time required by relevant national or local health authorities, whichever is longer. After that period of time, the documents may be destroyed, subject to local regulations.

No records may be disposed of without the written approval of the Sponsor. Written notification should be provided to the Sponsor prior to transferring any records to another party or moving them to another location.

Roche will retain study data for 25 years after the final study results have been reported or for the length of time required by relevant national or local health authorities, whichever is longer.

8. ETHICAL CONSIDERATIONS

8.1 COMPLIANCE WITH LAWS AND REGULATIONS

This study will be conducted in full conformance with the ICH E6 guideline for Good Clinical Practice and the principles of the Declaration of Helsinki, or the applicable laws and regulations of the country in which the research is conducted, whichever affords the greater protection to the individual. The study will comply with the requirements of the ICH E2A guideline (Clinical Safety Data Management: Definitions and Standards for

Expedited Reporting). Studies conducted in the United States or under a U.S. Investigational New Drug (IND) Application will comply with U.S. FDA regulations and applicable local, state, and federal laws. Studies conducted in the European Union or European Economic Area will comply with the E.U. Clinical Trial Directive (2001/20/EC) and applicable local, regional, and national law.

8.2 INFORMED CONSENT

The Sponsor's sample Informed Consent Form (and ancillary sample Informed Consent Forms such as an Assent Form or Mobile Nursing Informed Consent Form, if applicable) will be provided to each site. If applicable, it will be provided in a certified translation of the local language. The Sponsor or its designee must review and approve any proposed deviations from the Sponsor's sample Informed Consent Forms or any alternate consent forms proposed by the site (collectively, the "Consent Forms") before IRB/EC submission. The final IRB/EC-approved Consent Forms must be provided to the Sponsor for health authority submission purposes according to local requirements.

If applicable, the Informed Consent Form will contain separate sections for any optional procedures. The investigator or authorized designee will explain to each patient the objectives, methods, and potential risks associated with each optional procedure. Patients will be told that they are free to refuse to participate and may withdraw their consent at any time for any reason. A separate, specific signature will be required to document a patient's agreement to participate in optional procedures. Patients who decline to participate will not provide a separate signature.

The Consent Forms must be signed and dated by the patient or the patient's legally authorized representative before his or her participation in the study. The case history or clinical records for each patient shall document the informed consent process and that written informed consent was obtained prior to participation in the study.

The Consent Forms should be revised whenever there are changes to study procedures or when new information becomes available that may affect the willingness of the patient to participate. The final revised IRB/EC-approved Consent Forms must be provided to the Sponsor for health authority submission purposes.

Patients must be re-consented to the most current version of the Consent Forms (or to a significant new information/findings addendum in accordance with applicable laws and IRB/EC policy) during their participation in the study. For any updated or revised Consent Forms, the case history or clinical records for each patient shall document the informed consent process and that written informed consent was obtained using the updated/revised Consent Forms for continued participation in the study.

A copy of each signed Consent Form must be provided to the patient or the patient's legally authorized representative. All signed and dated Consent Forms must remain in each patient's study file or in the site file and must be available for verification by study monitors at any time.

For sites in the United States, each Consent Form may also include patient authorization to allow use and disclosure of personal health information in compliance with the U.S. Health Insurance Portability and Accountability Act (HIPAA) of 1996. If the site utilizes a separate Authorization Form for patient authorization for use and disclosure of personal health information under the HIPAA regulations, the review, approval, and other processes outlined above apply except that IRB review and approval may not be required per study site policies.

8.3 INSTITUTIONAL REVIEW BOARD OR ETHICS COMMITTEE

This protocol, the Informed Consent Forms, any information to be given to the patient, and relevant supporting information must be submitted to the IRB/EC by the Principal Investigator and reviewed and approved by the IRB/EC before the study is initiated. In addition, any patient recruitment materials must be approved by the IRB/EC.

The Principal Investigator is responsible for providing written summaries of the status of the study to the IRB/EC annually or more frequently in accordance with the requirements, policies, and procedures established by the IRB/EC. Investigators are also responsible for promptly informing the IRB/EC of any protocol amendments (see Section 9.6).

In addition to the requirements for reporting all adverse events to the Sponsor, investigators must comply with requirements for reporting serious adverse events to the local health authority and IRB/EC. Investigators may receive written IND safety reports or other safety-related communications from the Sponsor. Investigators are responsible for ensuring that such reports are reviewed and processed in accordance with health authority requirements and the policies and procedures established by their IRB/EC, and archived in the site's study file.

8.4 CONFIDENTIALITY

The Sponsor maintains confidentiality standards by coding each patient enrolled in the study through assignment of a unique patient identification number. This means that patient names are not included in data sets that are transmitted to any Sponsor location.

Patient medical information obtained by this study is confidential and may be disclosed to third parties only as permitted by the Informed Consent Form (or separate authorization for use and disclosure of personal health information) signed by the patient, unless permitted or required by law.

Medical information may be given to a patient's personal physician or other appropriate medical personnel responsible for the patient's welfare, for treatment purposes.

Given the complexity and exploratory nature of exploratory biomarker analyses, data derived from these analyses will generally not be provided to study investigators or patients unless required by law. The aggregate results of any conducted research will be available in accordance with the effective Sponsor policy on study data publication (see Section 9.5).

Data generated by this study must be available for inspection upon request by representatives of national and local health authorities, Sponsor monitors, representatives, and collaborators, and the IRB/EC for each study site, as appropriate.

Study data, which may include data on genomic variants, may be submitted to government or other health research databases or shared with researchers, government agencies, companies, or other groups that are not participating in this study. These data may be combined with or linked to other data and used for research purposes, to advance science and public health, or for analysis, development, and commercialization of products to treat and diagnose disease. In addition, redacted Clinical Study Reports and other summary reports will be provided upon request.

8.5 FINANCIAL DISCLOSURE

Investigators will provide the Sponsor with sufficient, accurate financial information in accordance with local regulations to allow the Sponsor to submit complete and accurate financial certification or disclosure statements to the appropriate health authorities. Investigators are responsible for providing information on financial interests during the course of the study and for 1 year after completion of the study (see definition of end of study in Section 3.2).

9. STUDY DOCUMENTATION, MONITORING, AND ADMINISTRATION

9.1 STUDY DOCUMENTATION

The investigator must maintain adequate and accurate records to enable the conduct of the study to be fully documented, including, but not limited to, the protocol, protocol amendments, Informed Consent Forms, and documentation of IRB/EC and governmental approval. In addition, at the end of the study, the investigator will receive the patient data, including an audit trail containing a complete record of all changes to data.

9.2 PROTOCOL DEVIATIONS

The investigator should document and explain any protocol deviations. The investigator should promptly report any deviations that might have an impact on patient safety and data integrity to the Sponsor and to the IRB/EC in accordance with established IRB/EC

policies and procedures. The Sponsor will review all protocol deviations and assess whether any represent a serious breach of Good Clinical Practice guidelines and require reporting to health authorities. As per the Sponsor's standard operating procedures, prospective requests to deviate from the protocol, including requests to waive protocol eligibility criteria, are not allowed.

9.3 SITE INSPECTIONS

Site visits will be conducted by the Sponsor or an authorized representative for inspection of study data, patients' medical records, and eCRFs. The investigator will permit national and local health authorities; Sponsor monitors, representatives, and collaborators; and the IRBs/ECs to inspect facilities and records relevant to this study.

9.4 ADMINISTRATIVE STRUCTURE

This trial will be sponsored and managed by Genentech, a member of the Roche Group. The Sponsor will provide clinical operations management, data management, and medical monitoring.

Approximately 20–30 sites globally will participate to enroll approximately 75 patients. Enrollment will occur through an IxRS.

Central facilities will be used for certain study assessments throughout the study (e.g., specified laboratory tests, biomarker and PK analyses), as specified in Section 4.5. Accredited local laboratories will be used for routine monitoring; local laboratory ranges will be collected.

9.5 DISSEMINATION OF DATA AND PROTECTION OF TRADE SECRETS

Regardless of the outcome of a trial, the Sponsor is dedicated to openly providing information on the trial to healthcare professionals and to the public, at scientific congresses, in clinical trial registries, and in peer-reviewed journals. The Sponsor will comply with all requirements for publication of study results. Study data may be shared with others who are not participating in this study (see Section 8.4 for more details), and redacted Clinical Study Reports and other summary reports will be made available upon request, provided the requirements of Roche's global policy on data sharing have been met. For more information, refer to the Roche Global Policy on Sharing of Clinical Trials Data at the following website:

www.roche.com/roche_global_policy_on_sharing_of_clinical_study_information.pdf

The results of this study may be published or presented at scientific congresses. For all clinical trials in patients involving an IMP for which a marketing authorization application has been filed or approved in any country, the Sponsor aims to submit a journal manuscript reporting primary clinical trial results within 6 months after the availability of the respective Clinical Study Report. In addition, for all clinical trials in patients involving

an IMP for which a marketing authorization application has been filed or approved in any country, the Sponsor aims to publish results from analyses of additional endpoints and exploratory data that are clinically meaningful and statistically sound.

The investigator must agree to submit all manuscripts or abstracts to the Sponsor prior to submission for publication or presentation. This allows the Sponsor to protect proprietary information and to provide comments based on information from other studies that may not yet be available to the investigator.

In accordance with standard editorial and ethical practice, the Sponsor will generally support publication of multicenter trials only in their entirety and not as individual center data. In this case, a coordinating investigator will be designated by mutual agreement.

Authorship will be determined by mutual agreement and in line with International Committee of Medical Journal Editors authorship requirements. Any formal publication of the study in which contribution of Sponsor personnel exceeded that of conventional monitoring will be considered as a joint publication by the investigator and the appropriate Sponsor personnel.

Any inventions and resulting patents, improvements, and/or know-how originating from the use of data from this study will become and remain the exclusive and unburdened property of the Sponsor, except where agreed otherwise.

9.6 PROTOCOL AMENDMENTS

Any protocol amendments will be prepared by the Sponsor. Protocol amendments will be submitted to the IRB/EC and to regulatory authorities in accordance with local regulatory requirements.

Approval must be obtained from the IRB/EC and regulatory authorities (as locally required) before implementation of any changes, except for changes necessary to eliminate an immediate hazard to patients or changes that involve logistical or administrative aspects only (e.g., change in Medical Monitor or contact information).

Appendix 1 Schedule of Activities

	Screening	In-Clinic Treatment		Surgery ^a	Post-Surgery Visit ^k
Day (Window)	(Day -28 to Day -1)	1	8 (±2)	15 (±2)	43 (±1 week)
Informed consent (Section 4.5.1) ^b	x				
Medical history, demographic data and baseline conditions (Section 4.5.2)	x				
Physical examination (Section 4.5.3)	x				x ^c
Height	x				
Weight	x				
Vital signs (Section 4.5.4)	x	x	x	x	x
ECOG performance status (Section 4.5.5)	x	x		x	x
Hematology (Section 4.5.9)	x ^d	x ^d	x	x	
Chemistry (Section 4.5.9)	x ^d	x ^d	x	x	
Coagulation (PT, aPTT, and INR) (Section 4.5.9)	x ^d	x ^d	x	x	x
FSH (Section 4.5.9) ^e	x				
Estradiol (Section 4.5.9) ^e	x				
Triplicate 12-lead ECG (Section 4.5.10)	x	x	x ^f	x ^f	
Tumor evaluation (Section 4.5.6)	x				
Tumor tissue (Section 4.5.9)	x			x or biopsy on Day 14	
Confirmation of available tissue sample	x				
Urinalysis (Section 4.5.9)	x				

GDC-9545—Genentech, Inc.
80/Protocol GO40987, Version 4

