concentration–time curve [AUC], respectively), with adverse organ effects largely confined to the kidney and liver. Although associated with the observation of PLD, it is unclear whether these toxicities were caused by PLD. In rats, PLD was not noted at 10 mg/kg (18-fold exposure factor), but increased in incidence and severity from 30 to 100 mg/kg. In monkeys, dose-responsive PLD was present at all doses but was limited to minimal changes in the lung at 20 mg/kg (6-fold exposure factor).

The translatability of PLD from nonclinical species to patients is not certain (Reasor et al. 2006). Drugs such as tamoxifen and palbociclib have not demonstrated any clinical concerns in spite of their PLD findings in nonclinical studies; thus, it is unclear whether GDC-9545-related PLD observed nonclinically will translate into a clinical finding in humans and whether this will have any clinical sequelae if it does. Although GDC-9545 was associated with PLD in multiple tissues in both rats and monkeys, there was no light microscopic evidence of involvement of critical organs such as heart, eyes, or neurons in these studies (Chatman et al. 2009). There is currently no qualified biomarker for assessment of PLD in the clinical setting although bis(monoacylglycerol)phosphate is being suggested as a potential biomarker; however, the function of the organs in which GDC-9545–related PLD may have been associated with toxicity in the 28-day rat and cynomolgus monkey studies (liver and kidney) is readily monitorable in the clinic using standard laboratory assessments.

No respiratory or neurobehavioral abnormalities were detected in rats or cynomolgus monkeys during the 4-week repeat-dose toxicity studies, with the exception of decreased locomotor activity that was only observed in rats at the high dose of 100 mg/kg/day.

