1.2.2 Clinical Summary

As of the data cutoff date of 1 February 2019, a total of 55 postmenopausal women with locally advanced or metastatic ER-positive (HER2-negative) breast cancer, including 29 patients in single-agent dose escalation, 6 patients in palbociclib-combination dose escalation, and 20 patients in single-agent dose expansion, had received at least one dose of GDC-9545 in Study GO39932. During dose escalation, 4 single-agent cohorts of 3 patients each were enrolled at 10-, 30-, 90-, and 250-mg doses, given once daily. To acquire additional PK, pharmacodynamic (PD), and safety data, up to 7 additional patients were enrolled to backfill single-agent dose-escalation cohorts at 10-, 30-, and 90-mg doses. The single-agent dose escalation completed enrollment in October 2018. No dose limiting toxicities (DLTs), related serious adverse events, or adverse events of special interest were reported. The MTD was not determined. Two dose levels of GDC-9545 were chosen for the single-agent dose expansion, 100 and 250 mg \pm LHRH agonist, and an escalation cohort combining 100 mg GDC-9545 with 125 mg palbociclib was enrolled.

GDC-9545 is tolerated well at all dose levels. The most frequently reported adverse events related to GDC-9545 in $\geq 10\%$ of patients were fatigue (15%), diarrhea and nausea (13%), and arthralgia (11%). Grade ≥ 3 adverse events were reported in 10 patients (18%), but all were considered unrelated to GDC-9545 by the investigators. Two patients have experienced serious adverse events considered not related to GDC-9545 by the investigator.

In Study GO39932, GDC-9545 was rapidly absorbed with peak concentrations achieved at 1–4 hours (mean time to maximum concentration) after single dose as well as at steady state. The geometric mean half-life after single dose ranged from 26.2–41.4 hours, indicating that once-daily dosing is appropriate for GDC-9545. In general, plasma exposures of GDC-9545 increased with doses at 10, 30, 90, and 250 mg after single and multiple doses. The expansion cohort's exposure was in line with escalation cohort exposure. Pharmacodynamics was assessed by functional imaging with [^{18}F]-fluoroestradiol-positron emission tomography and showed robust ER-target engagement across all doses.

Refer to the GDC-9545 Investigator's Brochure for details on nonclinical and clinical studies.

1.3 **STUDY RATIONALE AND BENEFIT–RISK ASSESSMENT**

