5.1.1.4 Renal Dysfunction

Dose-dependent effects on the kidneys were observed in repeat-dose studies in both rats and monkeys given GDC-9545. Microscopic findings consistent with renal injury were observed along with mild increases in creatinine, urea, and phosphorus. Some findings were reversible during the recovery phase in monkeys at the recovery dose assessed, but no reversibility was observed in rats. Please refer to the GDC-9545 Investigator's Brochure for further information.

Renal failure or acute kidney injury are not listed as unwanted effects of fulvestrant (eMC 2016a).

Renal function tests will be closely monitored in GDC-9545 studies with serum creatinine and BUN measurements.

Guidelines for management of patients with renal dysfunction are provided in [Table 1](#).

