5.1.2.3 Management Guidelines

Guidelines for management of specific adverse events are outlined in [Table 1](#). Additional guidelines are provided in the subsections below.

Table 1 Guidelines for Management of Patients Who Experience Specific Adverse Events

Event	Action to Be Taken
Elevation of hepatic transaminases	
 • Patients presenting with jaundice, coagulopathy, abdominal pain, or other symptoms suggestive of hepatic pathology should have their liver function tests checked and imaging of the liver performed. If the liver enzymes are elevated with no obvious malignant cause found, a hepatologist should be consulted. • Patients experiencing hepatic enzyme elevation should be treated and managed per standard of care. • Discontinue GDC-9545 for Grade ≥ 3 events and consult with the Medical Monitor.
Gastrointestinal toxicities (nausea, vomiting, diarrhea)	
 • Monitor patients closely for GI symptoms and the effects on their well-being. Patients experiencing nausea, vomiting, and diarrhea should be managed according to local standards of care, including use of anti-diarrheal agents and appropriate supportive care including hydration and dietary modification as appropriate. Infectious or alternate etiology should be excluded. • Discontinue GDC-9545 for Grade ≥ 3 events and consult with the Medical Monitor.
Venous thromboembolic events including pulmonary embolism	
 • Patients should be advised to seek immediate medical attention if they become aware of any symptoms of pulmonary embolism or DVT, such as acute onset of chest pain, shortness of breath, or swelling in extremities. • Manage and treat patients according to local standards of care (e.g., consider anti-coagulation and/or IVC filter). • Discontinue GDC-9545 for related VTE or pulmonary embolism and consult with the Medical Monitor.

Table 1 Guidelines for Management of Patients Who Experience Specific Adverse Events (cont.)

Event	Action to Be Taken
Renal toxicity (decrease in post-treatment GFR of >25% potentially attributed to GDC-9545)	
 • Patients experiencing deterioration in renal function should be treated and managed according to local standard of care. • Discontinue GDC-9545 and consult with the Medical Monitor.

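### No chemistry or hematology is scheduled after the surgery-day sample, so symptom-free liver or kidney changes that arise later, or are still unresolved, would not be systematically captured

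*Combined protocol and SAP*

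**What the plan says.** In Appendix 1, the rows "Hematology (Section 4.5.9" and "Chemistry (Section 4.5.9" are marked at screening, Day 1, Day 8 and surgery, with nothing at the post-surgery visit. The next row, "Coagulation (PT, aPTT, and INR) (Section 4.5.9", is marked in all five columns, including Day 43. Blood for ctDNA is also drawn at Day 43. Urinalysis is at screening only.

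Section 4.5.9 puts creatinine, BUN or urea, AST, ALT, bilirubin and ALP in the chemistry panel.

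The risk sections lean on these tests:

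- Section 1.2.1.2 identifies kidney and liver as the main sites of adverse organ effects in animals. Its reassurance is that the function of those organs ("liver and kidney) is readily monitorable in the clinic using standard laboratory assessments".
- Section 5.1.1.4 commits to monitoring: "Renal function tests will be closely monitored in GDC-9545 studies with serum creatinine and BUN measurements". Of the animal renal findings, it says that some reversed in monkeys, "but no reversibility was observed in rats".
- Section 5.2.3 lists Grade 3 or higher ALT/AST elevation, Grade 3 or higher renal failure and Hy's Law cases as adverse events of special interest. Section 5.4.2.2 makes them reportable until 28 days after the final dose.

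**The concern.** The schedule and the risk argument point in different directions. The protocol treats liver and kidney as the organs to watch and standard laboratory tests as the means of watching them. The last scheduled test of either organ nevertheless comes while the drug is still in the body. The test that is repeated at Day 43, coagulation, bears only indirectly on the liver and not at all on the kidney.

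Two kinds of change could go unseen: a rise without symptoms that starts after surgery, and a rise present at surgery that nobody records as an adverse event. Several adverse events of special interest are defined wholly or largely by laboratory values, and they are reportable over a period in which almost no chemistry is scheduled. The dose-level safety summary would then be silent on late or unresolved organ changes, in patients with operable disease who go on to surgery and further therapy.

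**Working it through.** The protocol states no figure to reproduce. The check is a reading of the schedule followed by timing arithmetic.

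**Count of scheduled panels (Appendix 1).**

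| Test | Screening | Day 1 | Day 8 | Surgery | Day 43 |
|---|---|---|---|---|---|
| Hematology | yes | yes | yes | yes | no |
| Chemistry | yes | yes | yes | yes | no |
| Coagulation | yes | yes | yes | yes | yes |
| Urinalysis | yes | no | no | no | no |

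Note d requires the Day 1 sample before dosing. Chemistry panels after dosing begins are therefore Day 8 and surgery, which makes 2. Panels after the surgery-day sample: 0. Nothing in Sections 4.5, 5 or 6 adds a scheduled one.

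**Is drug present at the last panel?** Section 3.1 asks for surgery within 24 hours of the last dose if possible, and Section 4.3.2 allows a dose on the morning of surgery. On half-life, Section 1.2.2 says: "The geometric mean half-life after single dose ranged from 26.2–41.4 hours". Assuming simple exponential decline at that rate, the fraction remaining after t hours is 0.5^(t / half-life).

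- At 24 h, half-life 26.2 h: 0.5^(24/26.2) = 0.53
- At 24 h, half-life 41.4 h: 0.5^(24/41.4) = 0.67

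So about 53% to 67% remains at 24 hours, and more if the last dose is taken on the day of surgery.

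**Time to washout (five half-lives).**

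- 5 × 26.2 / 24 = 5.5 days
- 5 × 41.4 / 24 = 8.6 days

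**Where the post-surgery visit falls.** Surgery is on Day 15 ± 2 (Day 13 to 17). The visit is on Day 43 ± 7 (Day 36 to 50).

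- Nominal gap: 43 − 15 = 28 days
- Shortest: 36 − 17 = 19 days
- Longest: 50 − 13 = 37 days

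Even at 19 days with the longer half-life, 0.5^(19 × 24 / 41.4) = 0.0005, or about 0.05%. A sample at a visit inside its window would be essentially drug-free. Note k can bring the visit forward if another anti-cancer therapy starts, so this is not guaranteed for every patient.

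**Coverage of the reporting period.** The surgery-day sample normally falls 0 to 1 day after the last dose. That leaves 27 to 28 of the 28 reporting days with no scheduled chemistry or hematology.

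**What unscheduled testing covers.**

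- Table 1 (Section 5.1.2.3) directs liver tests when symptoms suggest hepatic disease. Its renal row has no equivalent symptom trigger.
- Section 5.3.5.4 makes a laboratory result an adverse event if it brings symptoms, a treatment change or an intervention, or if the investigator judges it important. At surgery dosing is ending, so the treatment-change trigger largely falls away.
- Section 5.5.1 requires recorded adverse events to be followed to resolution or stability.

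What remains uncovered is the symptom-free change that begins after surgery, and the change at surgery that is not recorded as an adverse event.

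**The case against.** The best defense is that the protocol contradicts no promise and fails no stated objective. Section 2.1 asks for change from baseline in targeted laboratory tests, and Day 8 and surgery supply that. Reversibility is not an objective, and neither Section 1.2.1.2 nor Section 5.1.1.4 promises a post-washout panel. Section 3.3.2 assigns the traditional safety endpoints to Study GO39932. Section 1.2.2 reports 55 treated patients there, with no dose-limiting toxicities, related serious adverse events or adverse events of special interest. Section 5.1.1.1 says the hepatic changes in animals were reversible at all dose levels assessed. Day 43 values would also follow surgery, which complicates attribution.

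Most of this stands, and it limits the point. The reversibility argument rests mainly on the kidney, and the case for hematology is weaker than for chemistry. It does not explain why the post-surgery visit repeats coagulation, which is open to the same post-operative confounding, while omitting the panel that holds the liver and kidney tests.

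Three stronger readings are tempting and should be resisted:

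- A reader might infer that liver and kidney are never tested once exposure ends. The documents do not support that: the symptom-driven testing and adverse-event follow-up set out above can both produce later results, and Day 43 PT/INR is an indirect liver signal.
- A reader might rescale the 44-fold and 6-fold exposure factors in Section 1.2.1.2 to 100 mg and conclude that the safety margin is thin. Those factors describe exposures at which phospholipidosis was seen; the monkey value goes with minimal lung changes only. They are not liver or kidney toxicity margins.
- A reader might want a Day 43 value to serve Table 1's renal row ("decrease in post-treatment GFR of >25% potentially attributed to GDC-9545"). That row's action is to stop the drug, which has already ended by then.

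**Conclusion.** The gap is real but limited. Appendix 1 schedules two chemistry panels after dosing begins and none after the surgery-day sample, which is taken with roughly 53% to 67% of the drug still present at 24 hours. Symptom-free late changes, and surgery-day changes not recorded as adverse events, would not be systematically captured over 27 to 28 of the 28 reporting days. The mismatch is with the protocol's own reliance on laboratory monitoring of liver and kidney and with its laboratory-based events of special interest. It is not a breach of a stated objective. It does not undermine the study, but it is worth correcting because the visit and the blood draw already exist.

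The conclusion rests on the Appendix 1 cells as printed. The size of the residual exposure also assumes that the single-dose half-lives apply after repeated dosing; these are geometric means, so some patients will clear the drug more slowly.

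**What to change.** Reconcile Appendix 1 with Sections 1.2.1.2, 5.1.1.4, 5.2.3 and 5.4.2.2 by marking chemistry at the existing post-surgery visit. Hematology could be added as an option, but the documents support it less strongly. In Section 6.4, include the post-surgery value in the by-time laboratory display, shown by dose level. Report the actual number of days from last dose to sample, because the visit falls 19 to 37 days after surgery and note k can move it earlier. If the sponsor prefers to keep the present schedule, the protocol should say why coagulation is repeated and chemistry is not.

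The cost is an additional tube per patient at a visit where blood is already drawn, run at the local laboratory, with no new visit or procedure. The downside is that some post-operative changes will need interpretation before they can be attributed to the drug.
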